4.1.3. RADIATION THERAPY

4.1.3.1.Dose specifications/escalation

SRS will be delivered in 3 fractions. Provided that the MTD has not been reached, the total dose will be increased in 3 Gy increments:

Dose Level	Dose Per Fraction	Total Dose
1	8 Gy	24 Gy
2	9 Gy	27 Gy
3	10 Gy	30 Gy
4	11 Gy	33 Gy

A minimum of six patients will be enrolled per arm:

Arm	
1	4.2 - 14.1 cm ³ brain metastasis following surgical resection
2	14.2 - 33.5 cm ³ brain metastasis following surgical resection

Similar to RTOG 90-05, the dose limiting toxicity (DLT) is defined as grade 3, 4, or 5 RTOG central nervous system (CNS) acute radiation morbidity scoring criteria (Appendix C) observed within 30 days of radiosurgery. The MTD is defined as one dose level below the highest toxic dose (i.e., the DLT dose).

The occurrence of late toxicities will be continuously monitored. If a late DLT occurs in 3 or more out of 6 (or 4 or more out of 12) patients at a certain dose level after the radiation dose had already been escalated to the next level, the MTD will be backtracked to the level

below the one at which the DLTs occurred.

Number of Patients at a Given	Escalation Decision Rule					
Dose Level with a DLT						
0-1 out of 6	Enter 6 patients at the next higher dose level					
2 out of 6	Enter at least 6 more patients at the current dose level.					
	• If 0-1 of these 6 experience a DLT (i.e., 2-3					
	out of 12), then proceed to next dose level.					
	• If 2 or more of these 6 experience a DLT (4 or more out of 12), then dose escalation will be stopped. Six additional patients will be entered at the next lower dose level if only 6 patients were previously entered.					
3 or more out of 6	Dose escalation will be stopped. Six additional patients will be entered at the next lower dose level if only 6 patients were previously entered.					

Does escalation will proceed as follows, with minimum waiting period of 30 days before proceeding with the next higher dose level:

Should a patient not be evaluable at 30 days (due to death or loss to follow-up or discontinuation of the protocol follow-up per patient preference), then additional patients may be enrolled on each arm such that at least 5 of 6 are evaluable and experience no DLT. For example, should one patient be lost to follow up, but the remaining 5 patients have no DLT, then dose escalation may proceed.

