10. MEASUREMENT OF EFFECT

10.1 Anti-tumor Effect

Subjects will be seen in follow-up at 1, 3, 6, 9, and 12 months following SRS.At each follow-up, neurologic history and examination will be done. MRI with gadolinium will be obtained at 3, 6, 9, and 12 months.

10.1.1 **Definitions**

Early radiation toxicity is defined as those observed within 30 days of SRS. Late radiation toxicity is defined as those observed after 30 days following SRS. Tumor response will be measured using MRI with gadolinium obtained at 3, 6, 9 and 12 months following SRS.

10.1.2 **Disease Parameters**

Target lesion is defined as those treated with radiosurgery. The size and volume of the target lesion will be measured using the treatment planning software.

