10.2 Other Response Parameters

The primary endpoint of this study is to determine the MTD of tri-fraction SRS. The MTD is defined as one dose level below the highest toxic dose (i.e., the DLT dose). Similar to RTOG 90-05, the dose limiting toxicity (DLT) is defined as grade 3, 4, or 5 RTOG central nervous system (CNS) acute radiation morbidity scoring criteria (Appendix C) observed within 30 days of radiosurgery.

The occurrence of late toxicities will be continuously monitored. If a late DLT occurs in 3 or more out of 6 (or 4 or more out of 12) patients at a certain dose level after the radiation dose had already been escalated to the next level, the MTD will be backtracked to the level

below the one at which the DLTs occurred.

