11. DATA REPORTING / REGULATORY CONSIDERATIONS

11.1 Monitoring plan

Stanford Cancer Center (SCC) Data and Safety Monitoring Committee (DSMC) will be responsible for monitoring the research yearly and will operate independently from the clinical investigators. The primary responsibility of the DSMC is to review the reported study data to confirm it is accurate, complete, and verifiable from source documents. The DSMC will also confirm that the conduct of the trial maintains the safety and well being of human subjects, and is in compliance with the currently approved protocol, with GCP, and with applicable regulatory requirements. Study safety data will be reviewed by the DSMC in the form of summary reports or data listings on a regular basis.

11.2 Stopping rules (for the individual patient and for the study as a whole)

The dose limiting toxicity (DLT) is defined as grade 3, 4, or 5 RTOG central nervous system (CNS) acute radiation morbidity scoring criteria (Appendix C) observed within 30 days of radiosurgery.

The occurrence of late toxicities will be continuously monitored. If a late DLT occurs in 3 or more out of 6 (or 4 or more out of 12) patients at a certain dose level after the radiation dose had already been escalated to the next level, the MTD will be backtracked to the level below the one at which the DLTs occurred.

Number of Patients at a Given Dose Level with a DLT	Escalation Decision Rule
0-1 out of 6	Enter 6 patients at the next higher dose level
2 out of 6	 Enter at least 6 more patients at the current dose level. If 0-1 of these 6 experience a DLT (i.e., 2-3 out of 12), then proceed to next dose level. If 2 or more of these 6 experience a DLT (4 or more out of 12), then dose escalation will be stopped. Six additional patients will be entered at the next lower dose level if only 6 patients were previously entered.

Does escalation will proceed as follows:

3 or more out of 6	Dose escalation will be stopped. Six additional
	patients will be entered at the next lower dose level if
	only 6 patients were previously entered.

Should a patient not be evaluable at 30 days (due to death or loss to follow-up or discontinuation of the protocol follow-up per patient preference), then additional patients may be enrolled on each arm such that at least 5 of 6 are evaluable and experience no DLT. For example, should one patient be lost to follow up, but the remaining 5 patients have no DLT, then dose escalation may proceed.

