12.3 Sample Size

12.3.1 Accrual estimates

Six subjects per group will be enrolled at the starting dose for each of the four arms. Should a patient not be evaluable at 30 days (due to death or loss to follow-up or discontinuation of the protocol follow-up per patient preference), then additional patients may be enrolled on each arm such that at least 5 of 6 experience no DLT. The maximum number of subjects per arm will depend on the number of dose levels reached. If all four dose levels are reached, the maximum number of evaluable subjects in each arm is 30. If all four dose levels are reached for the all two arms of the study, the maximum number of subjects for the entire study is 60.

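### The six-patient expansion at the next lower dose has no decision rule for 30-day DLTs, so a level with 4 or more of 12 acute DLTs could be named the MTD

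*Combined protocol and SAP*

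**What the plan says.** The escalation table appears in 4.1.3.1 and again in 11.2. A DLT is a grade 3 to 5 event on the RTOG acute CNS scale, "observed within 30 days of radiosurgery". The rules that bear on this point are:

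- **First six, 0-1 DLT:** "Enter 6 patients at the next higher dose level".
- **First six, 2 DLTs:** six more at the same level. With 2-3 of 12 the arm escalates. "If 2 or more of these 6 experience a DLT (4 or more out of 12), then dose escalation will be stopped".
- **First six, 3 or more DLTs:** escalation stops.
- **After either kind of stop:** "Six additional patients will be entered at the next lower dose level if only 6 patients were previously entered".

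Section 10.2 (also 4.1.3.1) defines the result: "The MTD is defined as one dose level below the highest toxic dose (i.e., the DLT dose").

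One further rule can lower the MTD. It appears in 4.1.3.1, 10.2 and 11.2, and applies once the dose has been escalated past a level: "If a late DLT occurs in 3 or more out of 6 (or 4 or more out of 12) patients" at that level, the MTD moves to the level below. Section 10.1.1 fixes the time window: "Late radiation toxicity is defined as those observed after 30 days following SRS".

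Section 12 adds no decision rule. On size, 12.3.1 says: "If all four dose levels are reached, the maximum number of evaluable subjects in each arm is 30".

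**The concern.** The natural purpose of the expansion is to confirm the candidate MTD on 12 patients, yet no outcome in those six patients has a stated consequence for acute toxicity. A lower level that still has only six patients must have escalated with 0 or 1 DLT, so it never enters the table row that contains the 4-of-12 limit. The one rule that does revise the MTD after escalation is worded for late events.

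The same count at the same level is therefore treated in two ways. Four late DLTs in 12 lower the MTD; four acute DLTs in 12 do not. The MTD is the primary endpoint and is built on acute DLTs. As written, the trial could report as tolerated a dose with a DLT count that the protocol elsewhere treats as too toxic, or the investigators would have to settle the rule after seeing the data.

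**Working it through.** **1. Paths into the gap.** Suppose level k+1 stops the arm and level k has six patients. Level k then had 0 or 1 DLT in its first six. It reaches 4 or more of 12 in two ways:

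- 0 in the first six, then 4 or more in the next six;
- 1 in the first six, then 3 or more in the next six.

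A lower level that already has 12 patients had 2-3 of 12 and is not expanded, so the gap does not arise there.

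**2. What each rule does with that result.**

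| Rule | Applies? | Reason |
|---|---|---|
| 4 or more of 12 in the table | No | It sits under the 2-of-6 row; level k had 0-1 of 6 |
| Backtracking at 4 of 12 | No | Worded for late DLTs; 10.1.1 sets late as after 30 days |
| MTD definition | Yes | The highest toxic dose is still level k+1, so the MTD is level k |

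**3. Chance at a single level.** The documents state no DLT rate, so p is assumed. With X ~ Bin(6, p) and b(x) = P(X = x):

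P(4+ of 12 | 0-1 of first 6) = [b(0)·P(X≥4) + b(1)·P(X≥3)] / [b(0) + b(1)]

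| p | b(0) | b(1) | P(X≥4) | P(X≥3) | Numerator (joint) | Denominator | Conditional |
|---|---|---|---|---|---|---|---|
| 0.20 | 0.2621 | 0.3932 | 0.0170 | 0.0989 | 0.0433 | 0.6554 | 6.6% |
| 0.30 | 0.1176 | 0.3025 | 0.0705 | 0.2557 | 0.0856 | 0.4202 | 20.4% |
| 0.40 | 0.0467 | 0.1866 | 0.1792 | 0.4557 | 0.0934 | 0.2333 | 40.0% |

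For p = 0.30: 0.1176 × 0.0705 + 0.3025 × 0.2557 = 0.0083 + 0.0774 = 0.0856 before rounding of the terms, and 0.0856 / 0.4202 = 0.204. At p = 0.10 the conditional chance is 0.7%.

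**4. Chance over a whole arm.** This is an exact enumeration of the table over four dose levels. It counts arms whose named MTD has 4 or more acute DLTs in 12. All curves are assumptions.

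| DLT rates, levels 1-4 (%) | Share of all arms | Share of stopped arms |
|---|---|---|
| 2/5/10/15 | 0.06% | 0.5% |
| 5/10/15/20 | 0.4% | 1.6% |
| 5/10/20/40 | 3.0% | 4.0% |
| 10/20/30/40 | 6.7% | 7.8% |
| 10/20/35/50 | 9.1% | 9.5% |
| 15/25/35/45 | 8.9% | 9.4% |
| 20/30/40/50 | 10.4% | 10.6% |
| 25/35/45/55 | 11.3% | 11.3% |

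Stopped arms include those that stop at level 1, where there is no lower level to expand. Among arms that actually carry out the expansion the share is higher: 9.9% for 10/20/30/40 and 21.4% for 25/35/45/55.

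**5. Effect of a 4-of-12 rule.** For assumed rates of 10/20/30/45%, applying the rule and stepping down changes the chance of naming level 3 from 35.0% to 29.6%, level 2 from 35.2% to 38.5%, and level 1 from 17.9% to 19.9%.

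**6. Arm size.** The stated 30 equals 4 × 6 + 6, that is, four levels and one expansion. If level 4 stops the arm with six patients there and every level below holds six, expanding levels 3 and 2 gives 24 + 6 + 6 = 36, and expanding level 1 as well gives 42. With twelve patients at level 4 these become 42 and 48. Over the eight curves, a step-down rule adds 0.003 to 0.47 patients per arm on average.

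**The case against.** Three readings could close the gap.

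- **The row for 3 or more of 6.** Reaching 4 of 12 from 0-1 of 6 needs at least 3 DLTs in the new six. Applied to that cohort, this row would call for six patients one level down. But it is written as an escalation rule and does not reassign the MTD. Applied to the new six alone, it would also reject a level with 0 + 3 = 3 of 12, a total at which the table elsewhere allows escalation.
- **Late meaning after escalation.** A DLT is defined as a 30-day event, so a DLT after 30 days is a contradiction in terms. The backtracking rule's trigger and its 4-of-12 limit would suit an expansion. This ambiguity is real. However, the rule follows directly on a sentence about late toxicities, and 10.1.1 defines late toxicity by the 30-day mark.
- **Common sense and oversight.** Investigators with 4 of 12 would hardly call the level tolerated, and the DSMC reviews safety data. That is likely, but oversight is not a prespecified rule for the primary endpoint.

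On size, the larger shares need steep assumed curves, whereas section 2.6 calls the starting dose conservative. The conditional 20.4% and 40.0% apply to levels that pass with 0-1 of 6 only 42% and 23% of the time. With no target DLT rate in the protocol, 4 of 12 does not by itself prove the dose wrong. These limits stand, and they bear on how often the problem arises, not on whether the rule is missing.

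**Conclusion.** The concern holds. Followed as written, the protocol names as MTD an expanded level with 4 or more acute DLTs in 12. The event is rare if toxicity is low (0.06% of arms at 2/5/10/15%) and reaches about one arm in nine at 25/35/45/55%. All of these figures rest on assumed DLT rates and on independent outcomes with one common rate per level. The risk is greatest where the candidate MTD is itself toxic, which is where a confirming rule is most needed. This should be corrected. It does not undermine the rest of the escalation scheme, because escalation still stops as planned. Confidence is medium, because the wording of the backtracking rule leaves some room for another intention.

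**What to change.** Add one rule to 4.1.3.1, 10.2 and 11.2: an expanded level is declared the MTD only if 3 or fewer of its 12 patients have a DLT. Otherwise the MTD is the next lower level that meets the same rule, expanded to 12 if it has only six. If level 1 fails, the MTD is reported as not established. This reuses the protocol's own boundary between 3 and 4 of 12.

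Define a late DLT at the same time: name the scale and the time window, and state whether the backtracking rule also covers 30-day events seen after escalation.

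The cost is one sentence in three sections, plus revised maxima in the synopsis and 12.3.1, where 30 per arm and 60 overall would no longer hold. An arm could reach the sizes shown in the working, though the average increase is under half a patient. The reported MTD will occasionally be one or more levels lower, or not established.

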4.5 Criteria for Removal from Study

- Disease progression or death
- Intercurrent illness that prevents further administration of treatment: a condition, injury, or disease unrelated to cancer, that renders continuing of radiation treatment unsafe or regular study visits impossible.
- Unacceptable adverse event(s) (see adverse events)
- Patient decides to withdraw from the study
- General or specific changes in the patient's condition that render the patient ineligible for the study
- Non-compliance with protocol-required evaluations and study visits
- Inability of subject to comply with study requirements
- Determination by the investigator that it is no longer safe for the subject to continue therapy
- Patients who inadvertently become pregnant
- At the discretion of the treating investigators

Subjects who are discontinued from the study will still be followed for disease progression and survival.

Subjects who discontinue should, if possible, be seen and assessed by an investigator(s). The reason for withdrawal and the date of withdrawal must be documented.

If the reason for withdrawal from the trial is the death of the subject, the two options for categorizing withdrawal are either progressive disease or an adverse event (AE; more than one AE may be documented as a reason for withdrawal). Only one event will be captured as the cause of death. Note that death is an outcome and not an AE.

All trial treatment-related toxicities and serious adverse events (SAEs) must be followed up until resolution.

At withdrawal, all on-going study-related toxicities and SAEs must be followed until resolution, unless in the investigator's opinion, the condition is unlikely to resolve due to the subject's underlying disease.

Subjects/patients who discontinue from the study for reasons unrelated to the study (e.g., personal reasons, or adverse events after registration but prior to receiving study therapy) may be replaced as required for the study to meet its objectives. The decision

to remove a subject/patient and to replace dropouts will be made by the treating investigator. The replacement will generally receive the same treatment or treatment sequence (as appropriate) as the allocation number replaced.

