4.	Does one of the tumors mentioned in (3) have a volume of $4.2 - 33.5$ cm ³ ? (Yes)			
5.	Has the patient completed cytotoxic systemic therapy \geq 5 days prior to radiosurgery? (Yes)			
6.	Will cytotoxic systemic therapy be administered concurrent with SRS? (No)			
7.	Will the patient receive cytotoxic systemic therapy ≤5 days after the completion of SRS? (No)			
8.	Has the target metastatic lesion undergone previous SRS? (No)			

9.	Patient signed informed consent? (Yes)		
10	. Life expectancy of at least 12 weeks? (Yes)		
	Exclusion Criteria (From IRB approved protocol)		
1.	Has the patient previously been treated with whole brain irradiation? (No)		
2.	Has the metastatic lesion in question previously been treated with SRS? (No)		
3.	Does the patient have greater than 4 total brain metastases at the time of initial evaluation? (No)		
4.	Is the patient a pediatric patient (age <18), pregnant woman, or unable to give informed consent? (No)		

*All subject files must include supporting documentation to confirm subject eligibility. The method of confirmation can include, but is not limited to, laboratory test results, radiology test results, subject self-report, and medical record review.

IV. Statement of Eligibility

By signing this form of this trial I verify that this subject is [eligible / ineligible] for participation in the study. This study is approved by the Stanford Cancer Institute Scientific Review Committee, the Stanford IRB, and has finalized financial and contractual agreements as required by Stanford School of Medicine's Research Management Group.

Treating Physician Signature:	Date:
Printed Name:	/
Secondary Reviewer Signature:	Date:
Printed Name:	
Study Coordinator Signature:	Date:
Printed Name:	

a.

C. RTOG CNS ACUTE RADIATION MORBIDITY SCORING CRITERIA

- 0. No Change
- 1. Fully functional status (i.e., able to work) with minor neurologic findings. No medication needed.
- 2. Neurologic findings present sufficient to require home case; nursing assistance may be required; medications including steroids and anti-seizure agents may be required.
- 3. Neurologic findings requiring hospitalization for initial management.
- 4. Serious neurologic impairment which includes paralysis, coma, or seizures > 3 per week despite medication. Hospitalization required.
- 5. Death

D. RTOG CNS LATE RADIATION MORBIDITY SCORING CRITERIA

- 0. None
- 1. Mild headache; slight lethargy
- 2. Moderate headache; great lethargy

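### A death within 30 days is both a grade 5 DLT and a reason for being not evaluable, with no order of precedence, so a fatal toxicity can drop out of the DLT count

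*Combined protocol and SAP*

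**What the plan says.** **DLT rule.** Section 4.1.3.1 states that "the dose limiting toxicity (DLT) is defined as grade 3, 4, or 5 RTOG central nervous system (CNS) acute radiation morbidity scoring criteria" within 30 days. Section 10.2 repeats it as "grade 3, 4, or 5 RTOG central nervous system (CNS) acute radiation morbidity scoring criteria (Appendix C) observed within 30 days of radiosurgery", and section 11.2 gives the same definition. In Appendix C, grade 3 is "Neurologic findings requiring hospitalization for initial management", and grade 5 is the single word death, with no cause or attribution.

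**Evaluability rule.** Section 4.1.3.1 begins "Should a patient not be evaluable at 30 days (due to death or loss to follow-up" and goes on to list patient preference. The consequence, in the words of section 11.2, is that "additional patients may be enrolled on each arm such that at least 5 of 6 are evaluable and experience no DLT". Section 12.3.1 repeats the rule but omits the condition that the five patients be evaluable. The worked example in 4.1.3.1 and 11.2 covers one patient lost to follow-up and does not cover a death.

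**Section 4.5.** Its own replacement clause is limited to "Subjects/patients who discontinue from the study for reasons unrelated to the study". When a subject dies, "the two options for categorizing withdrawal are either progressive disease or an adverse event". The evaluability sentence carries neither limit and does not refer to 4.5.

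**The concern.** Two rules cover the same event in the same 30-day window and lead in opposite directions. Under the DLT definition, a death from CNS toxicity adds one to the count. Under the evaluability sentence, the same patient can be treated as not evaluable and another patient enrolled instead. Sections 4.1.3.1 and 11.2 contain both rules and do not rank them.

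The DLT count per level drives the escalation table, and the table yields the MTD. If the optional extra enrolment is used for a fatal toxicity, the count can only fall or stay the same, so the effect can only favour escalation. If a death from another cause is scored as grade 5, the effect can only hold escalation back. Two readers of the same cohort could therefore make different decisions, each consistent with the text.

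**Working it through.** The plan states no operating characteristics or event rates, so there is no figure of its own to reproduce. The check has two parts, and only the second needs assumptions.

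**1. Decisions under the protocol's own table**

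The table (4.1.3.1 and 11.2) escalates at 0–1 of 6, expands to 12 at 2 of 6 and stops at 3 or more of 6. Below, each fatal case had no earlier counted event, and each replacement is DLT-free.

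| Deaths | Non-fatal DLTs | Deaths counted | Deaths replaced |
|---|---|---|---|
| 1 | 0 | 1/6, escalate | 0/6, escalate |
| 1 | 1 | 2/6, expand | 1/6, escalate |
| 1 | 2 | 3/6, stop | 2/6, expand |
| 2 | 0 | 2/6, expand | 0/6, escalate |
| 3 | 0 | 3/6, stop | 0/6, escalate |

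A single death with five clean patients changes nothing. The decisions differ from the second event onward, unless non-fatal DLTs alone already reach three.

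**2. Chance of escalating past a level**

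Assumed inputs, none of them in the documents:
- nf: probability of a non-fatal DLT
- f: probability of a fatal toxicity within 30 days
- e: share of fatal cases already counted through an earlier grade 3 or 4 event

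Formulas, with X binomial (n = 6, per-patient probability p):
- P(escalate) = P(X ≤ 1) + P(X = 2) × P(X ≤ 1), the last factor being the second six patients
- Deaths counted: p = nf + f
- Deaths replaced: p = (nf + f·e) / (1 − f·(1 − e))

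Worked case, nf = 0.15, f = 0.05, e = 0:
- Counted: p = 0.20; P(X ≤ 1) = 0.655, P(X = 2) = 0.246; P(escalate) = 0.655 + 0.246 × 0.655 = 0.816.
- Replaced: p = 0.15/0.95 = 0.158; P(X ≤ 1) = 0.758, P(X = 2) = 0.188; P(escalate) = 0.758 + 0.188 × 0.758 = 0.900.

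| nf / f | Counted | Replaced, e = 0 | Replaced, e = 0.5 | Replaced, e = 0.8 |
|---|---|---|---|---|
| 5% / 2% | 0.991 | 0.997 | 0.994 | 0.992 |
| 10% / 2% | 0.954 | 0.971 | 0.963 | 0.958 |
| 15% / 5% | 0.816 | 0.900 | 0.860 | 0.834 |
| 20% / 10% | 0.556 | 0.764 | 0.657 | 0.595 |

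The gap between counting and replacing, in percentage points down the rows, is 0.6, 1.8, 8.4 and 21 at e = 0, and 0.1, 0.4, 1.8 and 3.9 at e = 0.8. At e = 1 the two rules agree. The replaced columns assume that the optional enrolment is always used.

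**The case against.** The strongest reply is that the two rules do not overlap when read sensibly. Grade 5 sits on a CNS radiation morbidity scale, so it means death from that morbidity. The other reasons for non-evaluability, loss to follow-up and patient preference, leave the DLT outcome unknown, so death in that list should mean death before the outcome could be judged. This reading is plausible and may be what the authors intended. It is still inference: no section states it, and none gives a criterion for separating a CNS-toxic death from any other. Section 4.5 shows that the authors could write a causal limit when they wanted one.

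A second reply is that the sentence only permits extra enrolment and never says that an event meeting the DLT definition is removed. That is correct. But it does not say that the event stays either, and calling a patient not evaluable, then filling the cohort with another, is naturally read as taking that patient out of the six.

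Third, other provisions bear on deaths: one cause is captured per death (4.5), adverse events carry an attribution scale (7.2.1.1), and an independent committee reviews safety data (11.1). These mean the facts of each death should be on record. None says how they feed the DLT count.

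Fourth, the larger gaps rest on assumed rates. This stands. Because grade 3 requires only a hospital admission for neurologic findings, many fatal cases may already have been counted, and the gap is then small. Three fatal toxicities among six patients would be rare: the binomial chance of three or more is about 0.015% at a 2% fatal rate and 1.6% at 10%.

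**Conclusion.** The concern holds. The text gives two treatments for a death within 30 days and no precedence between them, in the rule that sets the primary endpoint. The reading that separates toxic deaths from other deaths is plausible but unwritten.

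The divergence in decisions follows from the protocol's own table and needs no assumed rates. It requires at least two events in a cohort, at least one of them a death. The probability gap, about 0.1 to 21 percentage points, depends wholly on the assumed rates, on how many fatal cases were already counted, and on replacement being used each time. The top of that range needs a 10% fatal rate and no fatal case with an earlier counted event. This should be fixed: the triggering events may be uncommon, but they are fatal ones, and the correction is cheap.

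**What to change.** Reconcile the DLT definition (4.1.3.1, 10.2, 11.2 and Appendix C) with the evaluability sentence (4.1.3.1, 11.2 and 12.3.1) so that each 30-day death enters exactly one count. The criterion should be fixed before the escalation decision, worded identically throughout, and consistent with the death categories and replacement clause in 4.5. The same edit can align 12.3.1 with the other two versions of the evaluability sentence. Which rule applies is for the sponsor to decide.

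Also report each dose level's DLT tally with all 30-day deaths counted, so that a reader can see whether the classification affected a decision.

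The cost is one harmonised sentence and one extra tally per level. The small downside is that each 30-day death must be classified before escalation can be decided.
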